Appendix 5. Modified Response Evaluation Criteria in Solid Tumors (mRECIST), Version 1.1

This scale is used for the assessment of brain lesion response.

Modifications to RECIST v1.1 for Assessment of Brain Lesions

The modifications to RECIST v1.1 impact the number and the minimal size of the target brain lesions selected at baseline. Up to 5 lesions may be selected as target lesions; all brain lesions beyond these 5 target lesions will be regarded as nontarget lesions. Measurable lesions are defined as those that can be accurately measured in at least 1 dimension with the longest diameter ≥ 5 mm when evaluated with gadolinium-enhanced MRI.

Gadolinium-enhanced MRI is the only imaging modality accepted for the assessment of brain lesions.

- The technical specification of the MRI scanning sequence will be optimized for the evaluation of brain lesions, which must be measured in the same anatomic plane using the same imaging examinations. Whenever possible the same scanner should be used ([Eisenhauer et al, 2009](#)).
- As a modification to RECIST v1.1, target lesions as small as 5 mm may be selected, however the scanning should follow RECIST v1.1: contiguous slices of maximum thickness corresponding to half the size of the lesion. All measurements must be taken and recorded in millimeters (mm) using a ruler or calipers.
- Image Acquisition guidelines provide the slice thickness requirements that should be used following RECIST v1.1 criteria.

Evaluation of Target Brain Lesions

Definitions for assessment of target brain lesion(s) are as follows:

Complete Response (CR): Disappearance of all target lesions.

Partial Response (PR): At least a 30% decrease in the sum of diameters of target lesions, taking as reference the baseline sum diameters (e.g., percent change from baseline).

Stable Disease (SD): Neither sufficient shrinkage to qualify for PR nor sufficient increase to qualify for PD.

Progressive Disease (PD): At least a 20% increase in the sum of diameters of target lesions, taking as reference the *smallest sum of diameters* recorded since the treatment started (e.g., percent change from nadir, where nadir is defined as the smallest sum of diameters recorded since treatment start). In addition, the sum must have an absolute increase of at least 5 mm.

Not Evaluable (NE): Cannot be classified by 1 of the 4 preceding definitions.

Special Notes on the Assessment of Target Brain Lesions

If a target brain lesion disappears and reappears at a subsequent time point it should continue to be measured. The response at the time when the lesion reappears will depend upon the status of other lesions. For example, if the disease had reached a CR status then PD would be documented at the time of reappearance. However, if the response status were PR or SD, the diameter of the reappearing lesion should be added to the remaining diameters and response determined based on percent change from baseline and percent change from nadir.

Evaluation of Non-target Brain Lesions

Definitions for assessment of non-target brain lesion(s) are as follows:

Complete Response (CR): Disappearance of all non-target lesions.

Non-CR/Non-PD: The persistence of 1 or more non-target lesion(s) identified as a site of disease.

Progressive Disease (PD): Unequivocal progression of existing non-target lesions.

Not Applicable (NA): No non-target brain lesions at baseline.

Not Evaluable (NE): Cannot be classified by 1 of the 4 preceding definitions.

Special Notes on the Assessment of Non-target Brain Lesions

Non-target brain lesions that are not assessed at a particular timepoint based on the SoA (Table 3) should be excluded from the response determination (e.g., non-target response does not have to be “Not Evaluable”).

New Lesions

New brain malignancies denoting disease progression must be unequivocal. Lesions identified in follow up in an anatomical location not scanned at baseline are considered new lesions.

Any equivocal new lesion should continue to be followed. Treatment can continue at the discretion of the Investigator until the next scheduled assessment. If at the next assessment the new lesion is considered to be unequivocal, progression should be documented.

Time Point Response for Brain Lesions

Table A3 presents the intracranial response at an individual time point for all possible combinations of tumor response in target and non-target brain lesions, with or without the appearance of new brain lesions for patients with measurable (as defined in Section 7.2.1 and Section 7.2.2) intracranial disease at baseline.

Patients with a global deterioration of health status that requiring discontinuation of treatment without objective evidence of disease progression at that time should be classified as having

“symptomatic deterioration.” Objective response status is determined by evaluations of disease burden. Every effort should be made to document the objective progression even after discontinuation of treatment.

In some circumstances, it may be difficult to distinguish residual disease from normal tissue. When the evaluation of CR depends on this determination, it is recommended that the residual lesion be investigated (e.g., fine needle aspirate or biopsy) to confirm the CR.

Table A3: Evaluation of Brain Lesion Response

Target Lesions	Non-target Lesions	New Lesions	Response
CR	CR or NA	No	CR
CR	Non-CR/Non-PD or NE	No	PR
PR	Non-PD or NA or NE	No	PR
SD	Non-PD or NA or NE	No	SD
NE	Non-PD or NA or NE	No	NE
PD	Any	Yes or No	PD
Any	PD	Yes or No	PD
Any	Any	Yes	PD

Best Overall Brain Metastasis Response: All Time Points for Brain Lesions

The best overall brain metastasis response is defined as the best response recorded from the start of treatment until progression of brain metastasis and will be determined programmatically by the Sponsor based on the Investigator’s assessment of brain metastasis response at each time point. Only tumor assessments performed before the start of any subsequent anticancer therapies and not later than 30 days after last dose of study drug will be considered in the assessment of best overall brain metastasis response. Clinical deterioration or clinical progression noted on the completion eCRF will not be considered as documented disease progression.

To be assigned a status of brain metastasis SD, follow-up disease assessment must meet the SD criteria at least once after the first dose of study treatment for a minimum of 6 weeks.

If the minimum time for SD is not met, the best response will depend on subsequent assessments. For example, if an assessment of PD follows the assessment of SD and SD does not meet the minimum time requirement, the best response will be PD. Alternatively, patients lost to follow up after an SD assessment who do not meet the minimum time criterion will be considered NE.

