Any extracranial lesions that have been subjected to loco-regional therapies (e.g., radiotherapy, ablation, etc.) will not be considered measurable unless they have clearly progressed since the therapy. Previously treated lesions that have not progressed will be considered non-measurable and assessed as non-target lesions.

While FDG-PET scans are not required for this study, sites may perform extracranial imaging by PET-CT provided the CT is of similar diagnostic quality as CT performed without PET, including the use of oral and IV contrast media. If acquired according to local standards, FDG-PET may be used to document PD in accordance with RECIST v1.1.

The initial Screening imaging should be performed within 28 days of the first dose of study treatment. Post-Screening assessments will be performed as described in the SoA (Table 3) (± 7 days). **Imaging will not be delayed for delays in cycle start.** Every effort must be made to assess each lesion that is measured at Screening by the same method throughout the study to enable consistent comparison.

Confirmation of brain, extracranial and global CR and PR is required. Confirmation assessments must be performed no less than 4 weeks after the criteria for response have initially been met and may be performed at the next scheduled assessment. If a confirmation assessment is performed prior to the next scheduled assessment, the next scheduled evaluation is still required (i.e., regularly scheduled study visit evaluations must occur at each scheduled time point regardless of unscheduled assessments). Partial response can be confirmed at an assessment later than the next assessment after the initial documentation of PR. If the criteria for a CR or PR are not confirmed, then SD can be considered the best response if it has been demonstrated for a minimum of 6 weeks.

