7.2.2. Imaging Assessments for RECIST v1.1 and mRECIST v1.1

Details of response assessments are described in [Appendix 4](#), [Appendix 5](#) and [Appendix 6](#).

Brain lesions will be assessed by mRECIST v1.1 criteria. Modification of RECIST v1.1 allows up to 5 intracranial target lesions of 5 to 40 mm in diameter and includes target lesions measuring 5 to 10 mm in their longest diameter. Brain lesions will be measured only by gadolinium-enhanced MRI, with a scan-slice thickness of 1 mm for metastases with a longest diameter of 5 to 10 mm.

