A *sum of the diameters* (longest for non-nodal lesions, short axis for nodal lesions) for all target lesions will be calculated and reported as the *baseline sum diameters*. If lymph nodes are to be included in the sum, then as previously noted, only the *short* axis is added into the sum. The baseline sum diameters will be used as reference to further characterize any objective tumour regression in the measurable dimension of the disease.

All other lesions (or sites of disease) including pathological lymph nodes should be identified as *non-target lesions* and should also be recorded at baseline. Measurements are not required, and these lesions should be followed as ‘present’, ‘absent’, or in rare cases ‘unequivocal progression’ (more details to follow). In addition, it is possible to record multiple non-target lesions involving the same organ as a single item on the case record form (e.g., ‘multiple enlarged pelvic lymph nodes’ or ‘multiple liver metastases’).

Response Criteria

This section provides the definitions of the criteria used to determine objective tumour response for target lesions.

Evaluation of Target Lesions

Complete Response (CR): Disappearance of all target lesions. Any pathological lymph nodes (whether target or non-target) must have reduction in short axis to < 10 mm.

Partial Response (PR): At least a 30% decrease in the sum of diameters of target lesions, taking as reference the baseline sum diameters.

Progressive Disease (PD): At least a 20% increase in the sum of diameters of target lesions, taking as reference the *smallest sum on study* (this includes the baseline sum if that is the smallest on study). In addition to the relative increase of 20%, the sum must also demonstrate an absolute increase of at least 5 mm. The appearance of one or more new lesions is also considered progression.

Stable Disease (SD): Neither sufficient shrinkage to qualify for PR nor sufficient increase to qualify for PD, taking as reference the smallest sum diameters while on study.

Special Notes on the Assessment of Target Lesions

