Appendix 6. Criteria for Evaluation of Global Response

This appendix provides definitions for global assessment of target and non-target lesion(s).

Evaluation of Target Lesions

Target lesion response is based on all (i.e., brain and extracranial) target lesions, up to a total of 10 lesions. The sum of longest diameters of all target lesions will be used to determine response. Definitions for assessment of response for target lesion(s), based on mRECIST v1.1 for brain lesion and RECIST v1.1 for extracranial lesions, are as follows:

Complete Response (CR): Disappearance of all target lesions. Any pathological lymph nodes must be < 10 mm on the short axis.

Partial Response (PR): At least a 30% decrease in the sum of the diameters of target lesions, taking as a reference the baseline sum of the diameters (e.g., percent change from baseline).

Stable Disease (SD): Neither sufficient shrinkage to qualify for PR nor sufficient increase to qualify for PD.

Progressive Disease (PD): At least a 20% increase in the sum of the diameters of target lesions, taking as a reference the smallest sum of diameters recorded since the treatment started (i.e., percent change from nadir, where nadir is defined as the smallest sum of diameters recorded since treatment start). In addition, the sum must have an absolute increase from nadir of at least 5 mm.

Not Applicable (NA): No extracranial target lesions at baseline.

Not Evaluable (NE): Cannot be classified by 1 of the 5 preceding definitions.

Special Notes on the Assessment of Target Lesions

If lymph nodes are documented as target lesions, the short axis is added to the sum of the diameters (i.e., sum of diameters is the sum of the longest diameters for non-nodal lesions and the short axis for nodal lesions). When lymph nodes decrease to non-pathological size (i.e., short axis < 10 mm), they should still have a measurement reported in order not to overstate progression.

If at a given assessment time point all target lesions identified as baseline are not assessed, the sum of diameters cannot be calculated for purposes of assessing CR, PR or SD, or for use as the nadir for future assessments. However, the sum of the diameters of the assessed lesions and the percent change from nadir should be calculated to ensure that progression has not been documented. If an assessment of PD cannot be made, the response assessment should be NE.

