5.2.9. Adequate Baseline Tumor Assessment

An adequate baseline tumor assessment is defined as follows:

- Baseline assessments of all lesions (target, and non-target) must be within 28 days prior to or on the same day as date of first dose.
- All lesions (target and non-target) must have non-missing assessments.

Note: for target lesions, an actual measurement should be recorded and it should meet the criteria for being measurable and for non-target lesions the actual status at baseline should indicate that the lesion was present).

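### The brain and global criteria set the PD nadir from treatment start, contradicting Appendix 4's inclusion of the baseline sum; applied as written, early target growth can be called PD late or not at all

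*Protocol*

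**What the plan says.** The protocol states the PD reference for target lesions three times.

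- **Extracranial (Appendix 4, RECIST v1.1):** the reference is the smallest sum on study, and "this includes the baseline sum if that is the smallest on study".
- **Brain (Appendix 5, mRECIST v1.1):** the reference is the nadir, "where nadir is defined as the smallest sum of diameters recorded since treatment start". Baseline is not mentioned.
- **Global (Appendix 6):** PD is judged by "taking as a reference the smallest sum of diameters recorded since the treatment started", again without baseline.

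The baseline scan comes first. Protocol Section 7.2.1 says "The initial Screening imaging should be performed within 28 days of the first dose of study treatment", and SAP Section 5.2.9 says baseline lesion assessments "must be within 28 days prior to or on the same day as date of first dose".

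The protocol also limits what mRECIST is meant to change. Appendix 5 says "The modifications to RECIST v1.1 impact the number and the minimal size of the target brain lesions selected at baseline". Section 7.2.2 is to the same effect: "Modification of RECIST v1.1 allows up to 5 intracranial target lesions of 5 to 40 mm in diameter". Appendix 6 describes its target-lesion definitions as "based on mRECIST v1.1 for brain lesion and RECIST v1.1 for extracranial lesions". None of these announces a different progression reference.

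The SAP does not define the nadir. Section 6.1.2 derives best overall response (BOR) from Investigator assessments at each time point, and Section 3.2.2.5 takes PFS from Investigator-documented progression. Central review is optional (protocol Section 7.2.3).

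**The concern.** Two readings of brain progression can be defended from the same protocol. Under the Appendix 5 wording, the Week 4 sum is the first one in the reference set, so it is its own nadir and growth from baseline to Week 4 cannot be PD. Later growth is then measured from the already enlarged Week 4 sum. Under Appendix 4, the same growth in an extracranial lesion is PD.

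The patients affected are those whose disease grows from the outset. On the written rule their brain or global PFS can lengthen, and some can enter the disease control rate (DCR) as stable. Occasionally a later shrinkage could count as a confirmed brain response although progression had already occurred. Sites could apply different readings, and nothing in the SAP would reveal it.

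**Working it through.** **Inputs**

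- PD, all three appendices: sum ≥ 1.20 × reference and sum − reference ≥ 5 mm.
- Reference A (Appendix 4): minimum of baseline and all earlier post-baseline sums.
- Reference B (Appendices 5 and 6 as written): minimum of the sums since first dose. At the first scan the only such sum is the current one.
- PR: sum ≤ 0.70 × baseline, confirmed at least 4 weeks later.
- Scans (Schedule of Activities): Weeks 4 and 8, then every 8 weeks through Cycle 11.
- SD counts towards BOR only from 6 weeks (Appendix 5; SAP Section 6.1.2). SD at Week 4 alone does not qualify; SD at Week 8 does.

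**Plan's own figure.** The plan gives none on this point. As background, its decision rule (at least 21 responses in 50, 30% versus 50%) gives exact one-sided alpha 0.0478 and power 0.8987. That agrees with the stated 5% and about 90%, and does not depend on the nadir wording.

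**Direction.** A is the minimum over B's set plus baseline, so A ≤ B. Both PD conditions are easier to meet with a smaller reference, so target-sum PD under B is never earlier than under A. If the Week 4 sum is at or below baseline, A and B coincide from then on.

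**Worked sums** (illustrative; mm)

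| Baseline; Weeks 4, 8, 16 | Baseline counted (A) | As written (B) | Change |
|---|---|---|---|
| 25; 33, 35, 36 | Week 4: 33/25 = 1.32, +8, PD | 35/33 = 1.06, 36/33 = 1.09, SD throughout | BOR PD becomes SD; enters DCR |
| 30; 34.5, 39.7, 52.5 (15% per 4 weeks) | Week 8: 39.7/30 = 1.32, +9.7, PD | Week 8: 39.7/34.5 = 1.15, no; Week 16: 52.5/34.5 = 1.52, +18.0, PD | PD 8 weeks later; BOR PD becomes SD |
| 25; 31.3, 39.1 (25% per 4 weeks; to Week 8) | Week 4: 1.25, +6.3, PD | Week 8: 39.1/31.3 = 1.25, +7.8, PD | PD 4 weeks later; BOR PD both ways |
| 40; 52, 26, 26 | Week 4: 52/40 = 1.30, +12, PD | Week 4 SD; Weeks 8 and 16: 26/40 = 0.65, confirmed PR | Non-responder becomes responder |
| 40; 36, 44 (to Week 8) | Week 8: 44/36 = 1.22, +8, PD | Same | None |

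**DCR.** Let q be the share of patients whose only PD trigger by Week 8 is target growth over a baseline sum that is still the smallest. Let s be the share of those whose Week 8 sum is not PD against Week 4. DCR then rises by q × s. Neither value is in the documents. Letting s run from 0 to 1:

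- q = 0: no change.
- q = 2%: 0 to 2 points.
- q = 5%: 0 to 5 points.
- q = 10%: 0 to 10 points, or up to 50 × 0.10 = 5 patients in a cohort of 50.

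**Not affected.** New lesions or unequivocal non-target progression give PD at any scan under Tables A3 and A4. Duration of response is essentially untouched: a responder's nadir is already at or below 70% of baseline.

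**The case against.** The strongest reply is that Appendix 5 is RECIST v1.1 with two announced changes, lesion number and minimum size, and that Section 7.2.2 says the same. The only RECIST v1.1 progression rule reproduced in the protocol counts baseline. At the first scan baseline is also the only earlier measurement, so an experienced radiologist would probably use it. This stands as evidence that the exclusion is unintended, so a reader should not infer that the protocol has plainly adopted a baseline-excluding rule. It does not remove the problem. Appendix 5 writes out its own PD definition and defines the nadir explicitly, and readers and programmers tend to follow a specific definition.

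A second reply concerns the global endpoint. Extracranial growth is PD under Appendix 4, and Appendix 6 ends best global response at progression in either compartment. That narrows the exposure to brain growth and to the pooled target sum, which Appendix 6 still measures from treatment start.

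A third concerns DCR. It is tempting to say that every early grower is scored stable. That is wrong: a further rise of at least 20% and 5 mm by Week 8 still gives BOR PD, as in the third example.

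**Conclusion.** The point holds as an internal contradiction that should be resolved. If the Appendix 5 and 6 wording is applied, the error has one direction: brain and global target-sum PD can be dated later but never earlier. DCR can rise when Week 8 is not PD against Week 4. In rare cases a confirmed brain response could be counted after progression, which would matter only if the count lay near the threshold of 21.

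A reader might infer that PFS and DCR are overstated in this trial. The documents do not support that. It would require the literal wording to be used, and patients whose only early trigger is target growth without prior shrinkage. The plan gives no rate for either, so trial-level bias cannot be computed. Simulating patients who all grow steadily (assumed baseline sums of 10 to 50 mm and growth of 2 to 50% per four weeks, both uniform) dates PD later in 82% of them, by 4.4 weeks on average. Those figures describe an assumed subgroup of unknown size. The trial is planned around a 50% brain response rate, and patients who shrink first are unaffected.

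**What to change.** In Appendices 5 and 6, define the nadir as Appendix 4 does: the lowest target sum on study, with baseline counted when it is the lowest. State the same reference in the SAP.

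Add a programmed check that applies this rule to the recorded target sums and raises a query wherever the Investigator's time-point response disagrees. The Investigator assessment should remain the source of the endpoints. Replacing it with a programmed PD would change the planned derivation, which a missing clause does not justify.

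The cost is a clause in two appendices, a sentence in the SAP and one check on measurements already collected. No new data are needed. PFS and DCR may come out slightly less favourable; sample size, alpha and power do not change.
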